3.5 Complications

One week follow-up

The research nurse gives the patient and parents a symptom diary for recording symptoms (PDPH, headache, nausea, backache, fever & leaking or inflammation of the puncture site) for 8 days (day of the procedure and following week). After the week, the research nurse calls the parents and transfers the information to the study records.

Four-week follow-up

The research nurse or the investigator searches the patient's hospital records for potential complications that may be related to the procedure or the use of the system. The information is transferred to the study records.

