3.1 Participants

Pediatric hemato-oncology patients (aged from 18 months to 18 years) treated for acute lymphoblastic leukemia in Helsinki, Turku, and Tampere university hospitals are eligible for the study. Informed consent is obtained from all patients and/or their parents, depending on the child's age.

The goal is to gather data from at least 150 lumbar puncture (LP) procedures of at least 50 patients and ≤ 4 procedures per patient.

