3.3 Clinical procedure

Injeq's representatives gives a practical training session on the use of the equipment to principal investigators, other physicians, and research nurses before the patient recruitment begins.

All LP procedures included in the study are part of the patients' planned intrathecal treatment (IT) protocol. Lumbar punctures are performed under general anesthesia and physicians perform the procedures according to their normal schedules and otherwise normal practices.

After the CSF detection alarm, the physician removes the stylet and checks for a CSF flow through the needle. A physician can also perform the check based on his/her clinical judgement. The IT is delivered after the correct needle location is verified by the CSF flow and a CSF sample is taken for the laboratory analysis.

Study protocol & Statistical analysis plan, IQ-LP-03	Version 1
For ClinicalTrials.gov	
	Page 2 of 2

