3.6 Statistical analysis

Mean, median and min-max range are reported for the descriptive data, as appropriate.

The proportion of CSF samples with ≥ 10 erythrocytes/ μ L is reported with 95 % confidence interval.

The distribution of all CSF sample erythrocyte counts is reported as a cumulative distribution curve.

The first puncture success rate is reported with 95 % confidence interval.

The CSF detection sensitivity and false detection rates are reported with 95 % confidence intervals.

Confidence intervals are calculated with the exact Clopper-Pearson method.

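### Section 3.5 states no symptom record before the puncture, so diary frequencies of headache, nausea, backache and fever cannot separate existing from new symptoms

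*Combined protocol and SAP*

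**What the plan says.** Section 3.5 has two parts.

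- **One week.** Patients and parents receive a diary for recording "symptoms (PDPH, headache, nausea, backache, fever & leaking or inflammation of the puncture site". They keep it "for 8 days (day of the procedure and following week". Then "the research nurse calls the parents and transfers the information to the study records". The section does not say whether the diary is handed over before or after the puncture.
- **Four weeks.** Hospital records are searched for "potential complications that may be related to the procedure or the use of the system". This is the only wording on relatedness, and it belongs to the record search, not to the diary or the call.

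Section 3.1 describes children "treated for acute lymphoblastic leukemia" and aims for "at least 150 lumbar puncture (LP) procedures of at least 50 patients", with no more than four procedures from one patient. No minimum interval between included procedures is stated. Section 3.3 places every puncture within the child's "planned intrathecal treatment (IT) protocol" and under general anaesthesia. The case report form items named in section 3.4 cover system performance and the erythrocyte count, not symptoms.

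Section 3.6 names no symptom rate. The only sentence that could cover the diary is "Mean, median and min-max range are reported for the descriptive data, as appropriate".

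**The concern.** Four of the diary items (headache, nausea, backache and fever) are non-specific. In children being treated for leukaemia they can plausibly be present on the morning of a planned puncture. The procedure day counts as diary day one, but families are not asked to separate the hours before the puncture from the hours after it. A headache present at breakfast and one that starts in the evening can produce the same entry. A symptom persisting from an earlier procedure in the same child can be entered again.

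With no comparator described, nothing else in the study shows the background level. A record in the same child just before the puncture is the simplest reference available, and the plan does not state one. What is at stake is the reading of any symptom frequency reported under the heading of complications. Section 3.7 foresees both a journal paper and a report to the authorities, and a reader of either would naturally take such a frequency to mean symptoms that arose after the puncture.

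**Working it through.** **Text check.** The plan gives no symptom frequency, so there is no figure to reproduce. Three places could supply the missing separation:

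| Place | Would it separate existing from new symptoms? |
|---|---|
| 3.4, items on the case report form | No symptom item is named |
| 3.5, diary and nurse call | No record before the puncture and no sorting step stated |
| 3.5, four-week record search | Relatedness wording, but for hospital records only |

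Section 3.6 does not fill the gap at the analysis stage, since it has no symptom tabulation.

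**Illustration of size.** Every rate below is assumed; only the 150 procedures come from section 3.1.

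- r = proportion of procedures followed by a new symptom
- b = proportion with the same symptom already present, independent of r
- f = share of existing symptoms that enter the diary

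Proportion recorded: p = 1 − (1 − r)(1 − f·b). Overstatement: p − r = (1 − r)·f·b.

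| r | f | b = 5% | b = 10% | b = 20% |
|---|---|---|---|---|
| 10% | 1 | 14.5% | 19.0% | 28.0% |
| 10% | 0.5 | 12.25% | 14.5% | 19.0% |
| 10% | 0 | 10.0% | 10.0% | 10.0% |
| 5% | 1 | 9.75% | 14.5% | 24.0% |
| 5% | 0.5 | 7.375% | 9.75% | 14.5% |
| 20% | 1 | 24% | 28% | 36% |
| 20% | 0.5 | 22% | 24% | 28% |

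The largest overstatement at r = 10% is 0.90 × 1 × 0.20 = 18 points. At r = 5% it is 0.95 × 1 × 0.20 = 19 points, and at r = 20% it is 0.80 × 1 × 0.20 = 16 points.

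In procedures out of 150 at r = 10%, the excess 150 × (p − r) is 6.75 / 13.5 / 27.0 when all existing symptoms are recorded, 3.375 / 6.75 / 13.5 when half are, and 0 when none are.

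**The other direction.** The formula above allows only over-recording. Suppose instead that families leave out existing symptoms and also dismiss a new or worsened episode in a child who already had that symptom. The recorded proportion is then r(1 − b), and the loss is r·b. At r = 10% the loss is 0.5 / 1.0 / 2.0 points, or 0.75 / 1.5 / 3.0 procedures out of 150. This also rests on independence; if worsening is commoner in children with existing symptoms, the loss is larger.

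**The case against.** The strongest reply is that no planned estimate is touched. Section 3.6 gives confidence intervals to the erythrocyte proportion, first puncture success, detection sensitivity and the false detection rate. None uses the diary, and no symptom rate, comparison or safety threshold is named. This stands, and it limits the weight of the point.

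Next, the document is a short public version whose footer marks it for the trial registry. The diary form and the call script are not reproduced, and either might hold an onset item. This also stands: one can say only that the document does not state how the two kinds of symptom are separated.

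Third, the diary sits under headings about complications and follow-up, and the nurse's call gives a chance to clarify. That makes full recording of existing symptoms an upper bound rather than an expectation, but neither the headings nor the call amounts to a rule.

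Finally, a record before the puncture would not make a new symptom attributable to the needle. That is true, but separating new from existing symptoms is useful in itself.

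A reader might infer three stronger things that the documents do not support:

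- *The error can only overstate harm, so it could not hide a device problem.* That follows only from a model restricted to over-recording. With no rule, a worsened headache can be dismissed as the usual one.
- *PDPH and the puncture-site items are exempt.* Repeat procedures are allowed with no stated minimum interval, so carry-over of these items is not excluded.
- *The nurse's call a week later cannot recover the earlier state.* Nothing in the documents settles how well it could.

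**Conclusion.** The gap is real but modest. As written, section 3.5 yields diary frequencies that mix existing with new or worsened headache, nausea, backache and fever, including any carried over from an earlier procedure. Overstatement of new symptoms is the most likely result, though understatement is possible.

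The size cannot be derived from the documents. The range of 0 to 18 percentage points holds at an assumed 10% of new symptoms, with 5 to 20% existing, independence, and anything from none to all of the existing symptoms recorded. It extends to 19 points at 5% new. Because the range starts at zero, it shows what could happen, not that a material error will occur.

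The consequence arises only if symptom frequencies are reported from the diary. The point is a cheap improvement to what the complication data can show; it does not challenge the study's performance results.

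**What to change.** **Section 3.5.** State that the diary is handed over before each lumbar puncture, not once per child. Add a row headed *before the procedure today*, with the same symptoms and response options as the daily rows, so that the rest of the procedure day is entered separately. If the response options are only yes or no, worsening cannot be derived, and a graded option is needed.

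**Section 3.6.** For each symptom, report the number and proportion of procedures with new or worsened symptoms beside those with any recorded symptom. Count a symptom as new if it is absent in the added row and present later, and as worsened if a later entry is graded higher than that row. If the diary form already has an onset or baseline item, use it for this table and describe it in section 3.5.

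**Cost.** One extra diary row, earlier handover and one extra table, with no extra visit. The change does not separate effects of the needle from those of the intrathecal drug or the anaesthesia, and the report should say so.

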3.6 Statistical analysis

Mean, median and min-max range are reported for the descriptive data, as appropriate.

The proportion of CSF samples with ≥ 10 erythrocytes/ μ L is reported with 95 % confidence interval.

The distribution of all CSF sample erythrocyte counts is reported as a cumulative distribution curve.

The first puncture success rate is reported with 95 % confidence interval.

The CSF detection sensitivity and false detection rates are reported with 95 % confidence intervals.

Confidence intervals are calculated with the exact Clopper-Pearson method.

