3.7 Publication of results

- Peer-reviewed scientific report in a suitable journal.
- Confidential Clinical Investigation Report (CIR) is submitted for authorities.
- Conference abstracts or other relevant format may also be used to publish the results.

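### Does the absence of a stated summary for the complications leave the plan unable to report them?

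*Combined protocol and SAP*

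**What the plan says.** Section 3.5 sets up two sources of complication data. The first is a diary given to the family "for recording symptoms (PDPH, headache, nausea, backache, fever & leaking or inflammation of the puncture site) for 8 days", after which "the research nurse calls the parents and transfers the information to the study records". The second is a four-week search of the "hospital records for potential complications that may be related to the procedure or the use of the system".

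Section 3.6 then lists four proportions with 95% intervals: samples with at least 10 erythrocytes per microlitre, first puncture success, CSF detection sensitivity and false detection rate. It adds one cumulative curve of erythrocyte counts. Its general rule is "Mean, median and min-max range are reported for the descriptive data, as appropriate", and its interval rule is "Confidence intervals are calculated with the exact Clopper-Pearson method". Complications, symptoms and post-dural puncture headache are not mentioned there.

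Section 3.1 gives the size of the study as "at least 150 lumbar puncture (LP) procedures of at least 50 patients and ≤ 4 procedures per patient". Section 3.7 names a journal report and a report to regulators: "Confidential Clinical Investigation Report (CIR) is submitted for authorities". It does not describe their complication content.

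**The concern.** Each outcome in section 3.4 has a matching line in section 3.6, and the section 3.5 outcomes have none. The general line on mean, median and range is an odd fit for symptoms that are present or absent. The study tests a device in children and reports to authorities, so a safety figure defined only after the data are seen would be unwelcome.

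Several choices are left open:

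- whether the denominator is the procedure or the child;
- whether the diary window or the four-week window is used;
- how to count an event that appears in both sources, or that could belong to more than one procedure.

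There is also a statistical worry. An analyst who borrowed the section 3.6 interval method and applied it per procedure would treat up to four procedures in one child as independent. If complications cluster within children, the upper limit for a rare event would then look too tight.

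**Working it through.** **Text check.** Setting what is collected beside what is analysed:

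| Collected | Analysis named in section 3.6 |
|---|---|
| First puncture success (3.4) | Rate with 95% interval |
| Accuracy of CSF detection (3.4) | Sensitivity and false detection rate with 95% intervals |
| Erythrocyte count (3.4) | Proportion at or above 10 per microlitre with 95% interval; cumulative curve |
| Diary symptoms (3.5) | None named |
| Record-search complications (3.5) | None named |

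The omission is confirmed. None of the named analyses takes complication data as input, so none changes whatever summary is chosen. The plan states no complication figure that could be reproduced.

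**The denominator contrast.** Inputs are the section 3.1 targets, 150 procedures and 50 children. With zero events in n, the exact 95% upper limit is 1 − 0.025^(1/n):

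- n = 150 procedures: 1 − 0.025^(1/150) = 2.43%
- n = 50 children: 1 − 0.025^(1/50) = 7.11%

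The first bounds the risk per procedure. The second bounds the risk per child over all of that child's study procedures. At 150/50 = 3 independent procedures per child, the per-child limit converts to a per-procedure limit of 1 − (1 − 0.0711)^(1/3) = 2.43%. The two agree, so the threefold gap reflects the unit and not a loss of accuracy.

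**The clustering worry.** Assume 3 procedures per child and a within-child correlation r. The approximate effective sample size is 150/(1 + 2r), and the zero-event limit becomes:

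| r (assumed) | Effective n | Upper limit |
|---|---|---|
| 0 | 150.0 | 2.43% |
| 0.1 | 125.0 | 2.91% |
| 0.3 | 93.8 | 3.86% |
| 0.5 | 75.0 | 4.80% |
| 1 | 50.0 | 7.11% |

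The documents give neither a correlation nor an event rate. The table also describes an interval that section 3.6 does not propose for complications. It shows what a careless later choice could cost, not a fault in a planned analysis.

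**The counting window.** Section 3.5 ties the diary to the procedure day and the week after it, and ties the record search to complications of the procedure. The natural reading is follow-up per procedure. Whether two four-week windows overlap depends on the spacing of procedures, which the documents do not state.

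**The case for a change.** The strongest case for a change is that the remedy is short and the subject is safety. The general line does not name complications, and where section 3.6 wants a rate it says so and attaches an interval. Saying that the sponsor will report complications anyway does not settle which denominator or window will be used.

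Part of this stands. The document does not state the summary. A reader of the eventual report will need to see whether a percentage is per procedure or per child, and any per-procedure interval should allow for repeated procedures in the same child.

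The rest is weaker. The general line is qualified by its closing words and does not exclude complications, and the mean of a yes/no indicator is the rate. That is a thin reading, but it means that the plan does not bar a rate.

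Fuller rules would bring problems of their own:

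- **An interval per child only** mixes exposures, because children contribute one to four procedures. At an assumed independent risk of 5% per procedure, the per-child risk is 5% after one procedure and 1 − 0.95^4 = 18.5% after four.
- **Pooling the two sources** joins diary symptoms recorded without regard to cause with record-search events selected for possible relation to the procedure or system.
- **Assigning each event to the latest study procedure** needs onset dates that the documents do not show are recorded. It also ignores any non-study punctures in the child's treatment.

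**Conclusion.** The gap is real but calls for no change. It is reporting detail that analysts fill sensibly: a sponsor that collects these data and files an investigation report can be expected to give counts and percentages with their denominators. The effect on the planned estimates and intervals is nil.

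The contrast between 2.43% and 7.11% is a change of unit, and the two limits coincide under independence at three procedures per child. The intermediate values of 2.91% to 4.80% rest on assumed correlations, on the zero-event case and on an interval that the plan does not specify.

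The conclusion assumes that complications are reported as ordinary counts and percentages and that the unit is stated. Nothing in the documents points the other way. It covers only what this short public document says; the content of the confidential report cannot be seen from it.

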3.4 System performance assessment

After each LP procedure, the physician evaluates the system performance on a case report form (CRF). The first puncture success and accuracy of CSF detections are recorded.

First puncture success is defined as obtaining a CSF sample and/or successful IT with a single needle insertion; i.e., with one skin penetration. CSF detection sensitivity and False detection rate are defined as follows:

CSF detection sensitivity = # of correct CSF alarms / (# of correct CSF alarms + # of missing CSF alarms)

False detection rate = # of LP procedures with false alarms / # of all LP procedures

Erythrocyte count result (cells/ μ L) from the CSF sample is recorded on CRF.

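### Does basing the ≥10 erythrocytes/µL proportion on CSF samples, not on all lumbar punctures, bias the contamination rate low?

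*Combined protocol and SAP*

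**What the plan says.** Section 3.6 (Statistical analysis) reports "The proportion of CSF samples with ≥ 10 erythrocytes" per µL with a 95% Clopper-Pearson interval, and also plots the cumulative distribution of all counts. Section 3.4 (System performance assessment) says where the count comes from: the result "from the CSF sample is recorded on CRF". The denominator is therefore samples with a count.

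Three other statements bear on the point:

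- Section 3.4 defines first puncture success as "obtaining a CSF sample and/or successful IT" with one skin penetration, so a successful treatment without a sample is conceivable.
- Section 3.4 gives the false detection rate a different base, the number "of LP procedures with false alarms / # of all LP procedures".
- Section 3.3 (Clinical procedure) describes the usual sequence: "The IT is delivered after the correct needle location is verified by the CSF flow and a CSF sample is taken for the laboratory analysis".

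The recruitment goal in section 3.1 is "at least 150 lumbar puncture (LP) procedures of at least 50 patients and ≤ 4 procedures per patient". The plan states no expected contamination rate, no expected number of LPs without a sample, and no rule for them.

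**The concern.** The erythrocyte proportion can be computed only where the needle delivered CSF that was then analysed. A puncture that fails altogether, or gives too little fluid, contributes nothing. If such punctures tend to be traumatic, the proportion is conditional on partial success of the device under study: the more often the needle fails, the more unfavourable cases leave the calculation.

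This is an uncontrolled study in which the reported proportions and intervals are the result. A reader who took the figure as a rate per procedure could be misled. The false detection rate next to it does use all procedures, which makes the contrast look like an oversight. The natural remedy would be an all-procedure denominator with missing counts classed as unfavourable.

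**Working it through.** **No planned figure to reproduce.** The plan gives no hypothesis, target rate or precision goal for this endpoint. The arithmetic below only asks how far a sample-based figure could lie from an all-procedure figure.

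**Inputs.** N = 150 LPs is the minimum goal in section 3.1. The rest are assumptions: sampled rate p of about 20%; m = 3, 8 or 15 LPs without a count; and q, the unknown rate of counts ≥10/µL among those m.

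**Formulas.** With n = N − m and x samples at or above the threshold:

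- sample-based proportion = x/n
- all-procedure proportion = (x + q·m)/N
- difference (all-procedure minus sample-based) = (m/N)·(q − x/n)

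The sign of the difference is the sign of q − x/n. The sample-based figure is too low as a per-procedure rate if q exceeds the sampled rate, exact if they are equal, and too high if q is smaller.

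**Results for p of about 20%.**

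| m | Sample-based (95% CI) | All LPs, q = 0 | All LPs, q = 2p = 40% | All LPs, q = 1 |
|---|---|---|---|---|
| 3 | 29/147 = 19.7% (13.6–27.1) | 29/150 = 19.3% | 30.2/150 = 20.1% | 32/150 = 21.3% |
| 8 | 28/142 = 19.7% (13.5–27.2) | 28/150 = 18.7% | 31.2/150 = 20.8% | 36/150 = 24.0% |
| 15 | 27/135 = 20.0% (13.6–27.7) | 27/150 = 18.0% | 33/150 = 22.0% | 42/150 = 28.0% |

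The all-procedure figure is higher than the sample-based one by about 1.6, 4.3 and 8.0 points if every missing LP is bloody, and by about 0.4, 1.1 and 2.0 points at twice the sampled rate. It is lower by about 0.4, 1.1 and 2.0 points if none is bloody.

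**Yardstick.** The Clopper-Pearson interval at 30/150 is 13.9–27.3%, a half-width of (27.3 − 13.9)/2 = 6.7 points. Of the nine cases in the table, only 15 missing with all bloody exceeds it.

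**Other sampled rates, with m = 15.**

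| p | Sample-based | All LPs, q = 0 to q = 1 | All LPs, q = 2p | CI half-width at p, n = 150 |
|---|---|---|---|---|
| 10% | 14/135 = 10.4% | 9.3–19.3% | 11.3% | (16.0 − 5.7)/2 ≈ 5.2 |
| 30% | 40/135 = 29.6% | 26.7–36.7% | 32.7% | (38.0 − 22.8)/2 = 7.6 |
| 40% | 54/135 = 40.0% | 36.0–46.0% | 44.0% | (48.3 − 32.1)/2 = 8.1 |

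Even with a tenth of counts missing and twice the sampled rate among them, the shift (about 1, 3 and 4 points) stays inside the half-width.

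**The passages side by side.**

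- A cells/µL threshold needs a sample, so the count-based endpoint in section 3.6 fits its measurement in section 3.4.
- A false alarm can occur at any LP, so all LPs are the right base for the false detection rate. The two denominators differ because the quantities differ.
- A failed first insertion does not remove an LP from the erythrocyte figure. If a later insertion yields a sample, that sample counts, so some difficult procedures stay in.
- A puncture that yields neither sample nor treatment cannot meet the definition of first puncture success, which section 3.6 reports with its own interval.

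**The case for a change.** The strongest case for a change is that nothing in section 3.6 asks for the number of LPs without a count or the reasons, and that the sample-based proportion cannot reveal their number. In the table it stays near 20% while missing counts rise fivefold. The wording of the success definition admits LPs without a sample, and the plan does not say which sample is used if there are several.

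The omission is real, but it does not carry the argument far. The flat 20% is built into the example, because the sampled rate was held there by assumption. The admitted sample-less cases are successful treatments, which may have had clear flow and could push the difference the other way. That wholly failed punctures are bloodier is plausible, but the documents contain nothing to support it.

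An exact interval cannot be calculated without fixing n. The number of counts is therefore known at analysis, and the shortfall from all LPs follows by subtraction.

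**Conclusion.** The concern reads the text correctly: LPs without a count drop out, and the plan does not ask for their number. It does not show an error. The proportion of samples is a coherent, openly stated target, and a bias arises only if it is read as a per-procedure rate. The direction of that bias cannot be derived from the documents. Under the assumptions used (150 LPs, about 20% of samples at or above the threshold), its size is about 0.4 to 2.0 points for 3 to 15 missing counts at twice the sampled rate. It reaches 8.0 points only if 15 are missing and all are bloody. Section 3.3 makes sampling routine, which suggests few missing counts, though the documents give no number.

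Classing every missing count as unfavourable would be no gain. It would label treatment given through clear flow without a sample, or an unusable sample, as blood contamination, and so create a composite of failure and contamination. A split by first puncture success is an optional extra analysis.

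What remains is reporting detail that analysts ordinarily supply: LPs attempted, LPs with a sample and LPs with a count, with best-case and worst-case bounds over all LPs if more than a few counts are missing. None of this requires a change to the plan.

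### Every 95% interval is a plain Clopper-Pearson interval although a child may contribute up to four LPs; coverage can fall below 95% once the within-child correlation passes roughly 0.05–0.1, depending on the rate and the LPs per child

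*Combined protocol and SAP*

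**What the plan says.** Section 3.1 (Participants) sets the target as "at least 150 lumbar puncture (LP) procedures of at least 50 patients and ≤ 4 procedures per patient". At the two minimums that is 150/50 = 3 LPs per child on average, so repeat procedures are part of the design.

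Section 3.4 counts the false detection rate per LP and the CSF detection sensitivity per alarm. Neither is counted per child, and the sensitivity denominator need not equal the number of LPs.

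Section 3.6 gives a 95% interval to four proportions: samples with 10 or more erythrocytes/µL, first puncture success, CSF detection sensitivity and false detection rate. On the last two it says "The CSF detection sensitivity and false detection rates are reported with 95 % confidence intervals". One method then covers all four: "Confidence intervals are calculated with the exact Clopper-Pearson method". No section mentions within-patient correlation, a clustered interval or model, or an analysis of one LP per child.

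**The concern.** Clopper-Pearson limits guarantee at least 95% coverage when the count is binomial, that is, when the trials are independent with a common probability. LPs in the same child may not be independent, because the same anatomy and disease recur each time. A positive correlation makes the total count more variable than the binomial, so the interval is too narrow for its label.

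The documents contain no hypothesis test, success threshold or precision target. The four proportions with their intervals are therefore the only inferential results planned, and section 3.7 sends the results to a journal and to the authorities. What is at stake is whether an interval labelled 95% covers about 95%. The point estimates are not affected.

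**Working it through.** **Inputs from the documents.** At least 150 LPs, at least 50 patients and at most 4 LPs per patient (section 3.1); 95% Clopper-Pearson intervals (section 3.6).

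**Assumed, because the documents do not give them.** True rate p, ICC ρ, and how the LPs are spread over children. All three are shown as ranges.

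**Step 1: the plan's own figure.** With 150 independent LPs (ρ = 0), exact coverage averages 96.1% over p from 0.03 to 0.50, with a minimum of 95.0%. Results are symmetric in p and 1−p. The nominal 95% is met if LPs are independent.

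**Step 2: coverage with clustering.** Each child's count is beta-binomial with parameters p(1−ρ)/ρ and (1−p)(1−ρ)/ρ. Convolving over children gives the distribution of the total X. Coverage is the sum of P(X = x) over all x whose Clopper-Pearson limits contain p. The table shows the range over p = 0.75, 0.80, 0.90 and 0.95.

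| ICC | 150 LPs in 50 children (50×3 or 25×4 + 25×2) | 75×2 (150 LPs) | 50×4 (200 LPs) |
|---|---|---|---|
| 0 | 95.9–97.2% | 95.9–97.2% | 95.8–96.7% |
| 0.05 | 94.7–96.3% | 95.4–96.8% | 94.3–95.4% |
| 0.1 | 93.4–95.5% | 94.9–96.3% | 92.6–94.0% |
| 0.2 | 90.8–93.6% | 93.8–95.5% | 89.3–91.2% |
| 0.3 | 88.2–91.7% | 92.7–94.5% | 86.1–88.3% |

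These are selected rates. On a 0.01 grid from 0.75 to 0.95 the first column becomes 95.5–97.2% at ICC 0, 92.9–95.5% at 0.1 and 90.2–93.6% at 0.2, so the table slightly understates the shortfall.

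**Step 3: rates near 100%.**
- 150 LPs in 50 children, p = 0.97: 93.6–94.1% at ICC 0.2 and 91.4–92.2% at 0.3.
- The same designs, p = 0.98–0.99: 95.7–97.2% and 94.6–96.4%.
- 50×4, p = 0.98: 90.0% and 86.6%.

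**Step 4: where coverage first drops below 95%.** For 50×3 this happens at ICC 0.05 for p = 0.5, 0.7 or 0.8; 0.13 for 0.90; 0.07 for 0.95; 0.16 for 0.97; about 0.5 for 0.98; and about 0.3 for 0.99. Average coverage over p = 0.05–0.50 drops below 95% at ICC 0.04 for 50×4, 0.06 for 50×3 and 0.11 for 75×2.

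**Step 5: size on the reported scale.** The design effect is 1 + (m_A − 1)ρ, with m_A = Σm²/Σm (m = LPs per child), and the effective n is N divided by it. Clopper-Pearson limits are then taken at the effective n. At ICC 0.2 and an assumed observed rate of 80%:
- 50×3: 1 + 2 × 0.2 = 1.4; 150/1.4 = 107. The interval goes from 72.7–86.1% to 71.2–87.1%. Width 15.9 against 13.4 points, 19% wider.
- 75×2: 1 + 1 × 0.2 = 1.2; 150/1.2 = 125. It becomes 71.9–86.6%. Width 14.7 against 13.4, 10% wider.
- 50×4: 1 + 3 × 0.2 = 1.6; 200/1.6 = 125. It goes from 73.8–85.3% to 71.9–86.6%. Width 14.7 against 11.5, 28% wider.

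**The case against.** The strongest reply is that the decisive input is unknown. No ICC is stated, and section 3.3 points partly towards a low one: "Lumbar punctures are performed under general anesthesia and physicians perform the procedures according to their normal schedules". Anesthesia is therefore the same for every LP, and a child's LPs need not share an operator. This stands. It is why the conclusion is conditional.

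The number of repeats is not fixed either. Section 3.1 would equally allow 100 children with one LP and 25 with two. Coverage is then 94.8–96.6% at ICC 0.2 and 94.4–96.3% at 0.3 (p 0.75–0.95), and the planned interval is adequate. This also stands, but the plan does not commit to such a pattern, and its minimum targets imply three LPs per child.

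If first puncture success and sensitivity are close to 100%, Clopper-Pearson's built-in conservatism largely absorbs the clustering with 150 LPs in 50 children. That is correct, but it fails for 50×4 at p = 0.98. The plan also states no expected rates that would put all four proportions in the protected range.

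No stated decision depends on the intervals, and the limits move by about 1–2 points. Conceded; this sets the rating.

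Finally, this is a two-page version for ClinicalTrials.gov, and a fuller plan may exist. That weakens any inference from silence. The concern, however, rests on an explicit sentence that assigns an independent-trials method to clustered data.

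**Conclusion.** The concern holds, as a minor one. The missing allowance for clustering is certain from the text; that it matters in practice is only moderately likely, because the ICC, the expected rates and the spread of LPs over children are assumptions.

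At ICC 0.05–0.1 the loss is modest. From about 0.2 upwards, with two to four LPs per child and rates of 0.75–0.95, the intervals would usually cover less than 95%. They overstate precision somewhat: 10–28% too narrow a width in the 80% examples, or about 1–2 points on each limit. The cumulative distribution curve of erythrocyte counts has no planned interval and is not affected.

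**What to change.** Replace the Clopper-Pearson sentence in section 3.6 with wording such as:

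> Confidence intervals for all reported proportions allow for clustering within patient, using Clopper-Pearson limits at the effective sample size (Korn-Graubard type, without a degrees-of-freedom correction). The design effect is estimated from the patient-clustered variance for each proportion's own denominator and floored at 1. If the observed proportion is 0% or 100%, the ordinary Clopper-Pearson interval is reported, labelled as not adjusted for clustering, with the interval based on the number of contributing patients beside it as a worst-case bound.

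Add a sensitivity analysis of each child's first study LP (n ≥ 50). For CSF detection sensitivity this removes repeats only if each LP contributes one counted alarm. A patient-level bootstrap or a GEE with robust variance would also be acceptable, but each needs its own rule for 0% or 100%. Such a result is not remote: at p = 0.99 the chance of 150/150 is 0.99^150 = 22.1% with independent LPs.

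**Cost.** One sentence and a few lines of code. No new data are needed, since enforcing the cap of four already requires linking each LP to its patient. If the ICC is 0, intervals with 150 LPs in 50 children are on average 3.3–3.6% wider at p 0.75–0.95 and 0.8–1.0% wider at 0.99. A result of 150/150 would be shown as 97.6–100%, with a worst-case lower bound of 92.9% (50 patients). The first-LP analysis is imprecise: 40/50 gives 66.3–90.0%.

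**Performance and limits.** In 20,000 simulated trials per scenario, with 150 LPs in 50 children and p 0.75–0.95, the proposed interval covers 94.7–97.5% for ICC up to 0.2 and 93.7–96.2% at 0.3. Its weak point is 50×4 at p = 0.98: 94.0% at ICC 0.2 and 92.2% at 0.3, still better than the planned 90.0% and 86.6%. With few failures the design effect rests on one or two children: two failures at 148/150 give a lower limit of 92.7% if both are in one child, against 95.3% if they are in different children. It does not address clustering by operator or hospital.
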